After eligibility and written informed consent is confirmed patients will be randomized on the day of surgery after arrival at the OR to receive either fibrinogen concentrate or placebo after heparin reversal as indicated in the algorithm (Figure 3). If the patient has a diffuse medical bleed then the research coordinator will be called to inform The research coordinator study drug designate will call the study drug designate to randomize the patient and a sequential envelope will be opened by them in the blood bank. The drug/placebo will be prepared in the Blood Transfusion Services at the Infirmary site. The drug/placebo will be transported to the OR by the study drug designate.

Dosage and Dosage Regimen

The dose of fibrinogen concentrate will be calculated based on the point of care measurement of maximum clot firmness (MCF)

Capital Health

in the FIBTEM® test performed on CPB (aortic cross clamp off)¹⁰. According to the available literature we will use the following formula to achieve the preoperative (baseline) FIBTEM MCF (mm):

$$\text{Fibrinogen dosage (g)} = [\text{Preop FIBTEM MCF (mm)} - \text{FIBTEM MCF (mm)}] \times \text{bodyweight (kg)} \times c$$

$$C = \frac{0.5 \text{ g}}{1(\text{mm}) \times 70}$$

70

The formula can be simplified to:

$$(\text{Preop FIBTEM MCF} - \text{FIBTEM MCF}) \times \text{bodyweight}/140.$$

Calculation example: A patient's bodyweight is 75kg. The baseline FIBTEM MCF showed 22mm. The FIBTEM test on CPB shows a MCF of 10 mm. The overall dose of concentrated fibrinogen to achieve the baseline MCF of 22 mm would be:

$$\text{Fibrinogen dosage (g)} = (22 - 10) \times 75/140 = 12 \times 75/140 = \mathbf{6.4}$$

Fibrinogen dosing will be based on the results of the FIBTEM® analysis. The amount of fibrinogen concentrate corresponds to approximately 0.5 g of fibrinogen concentrate needed to raise MCF by 1 mm in a 70 kg patient^{9,10,26}. The maximum fibrinogen concentrate dose used in this study will be 10 g. If the baseline FIBTEM® is ≤ 12 mm the fibrinogen dosage will be calculated **from a minimum baseline value of 15 mm to achieve a more effective fibrinogen dosage**. In the placebo group, the standard hemostatic algorithm involving the use of plasma, Cryo and platelets (Figure 3), will be used as per the standard of care currently in place at CDHA.

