- intake of anti-clotting drugs within 2-5 days preoperatively (low dose ASA is allowed) based on the drug's half life or pharmacokinetic profile,
- allergy to concentrated fibrinogen or other components in the product,
- anemia (Hb < 110),
- diagnosed deep vein thrombosis (DVT),
- pulmonary embolism,
- acute stroke **(within the last 3 months)**,
- acute myocardial infarction (within the last 3 months),
- **any unstable medical condition as determined by the Principal Investigator**
- **within the past 30 days, participated in or currently enrolled in a clinical trial.**

Subject withdrawal criteria

Capital Health

As per the intraoperative algorithm (Figure 3) the Anesthesiologist and the Surgeon complete a bleeding assessment ten minutes after the protamine is given. If the patient is not having a diffuse medical bleed they will not be randomized and will be considered a screen failure. **Patients who are experiencing surgical bleeding after weaning from CPB and protamine administration with requirement of a second pump run are withdrawn from the study.** In case of an ongoing bleeding after step 3 of the study algorithm (Figure 3) an immediate and blinded FIBTEM is performed in order to prevent an overdosing of fibrinogen. If the FIBTEM shows an amplitude > 20 mm the patient will be unblinded and drop out of the study for safety reasons. This way it is ensured that a patient who received concentrated fibrinogen is not getting Cryoprecipitate (step 4 of study algorithm; Figure 3) leading to supraphysiologic levels of fibrinogen. Patients who have extremely rare complications like air embolism, heart perforation or heart lung machine failure will be ~~excluded~~ **withdrawn** from the study.

TREATMENT OF SUBJECTS

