As per the standard of care in this surgical population, all post-operative cardiac surgery patients will be taken immediately to a dedicated cardiovascular intensive care unit (CVICU). All patients will receive respiratory and hemodynamic support as needed. Each patient will be required to meet standard hospital criteria both prior to extubation and prior to transfer to the intermediate-care unit (IMCU). Discharged patients will be transferred to an intermediate-care unit or general-care ward under the care of the same cardiac surgical team. All patients will be monitored continuously for a minimum of 24 hours. In case of a post-operative bleeding in CVICU the same algorithm (Figure 3) like in the OR will be used. In case of surgical bleeding a re-sternotomy will be performed. Diffuse bleeding will be treated with blood components (step 2 -5, Figure 3). Patients having a valve replaced with a mechanical valve will receive heparin or warfarin 48 hours after surgery. All other patients will get ASA (acetylsalicylic acid, Aspirin®, Bayer Canada) on the first postoperative day (anticoagulation protocol, Division of Cardiac Surgery, QEII, Halifax, Canada).

ASSESSMENT OF SAFETY

Adverse Events

The following treatment-emergent and adverse effects will be captured during this study from the date ~~the consent was signed~~ of randomization to the 6 month follow-up:

Treatment-emergent adverse events

- Pleural effusion
- Atrial fibrillation
- Postoperative Delirium
- Reoperation because of surgical bleeding and unknown bleeding
- Air embolism

Adverse events (A/E) and Serious adverse events (SAE)

- Anaphylaxis
- Stroke
- Myocardial infarction
- Pulmonary embolism
- Deep vein thromboembolism
- Sternal wound infection
- Recurrent angina
- Angiography
- Percutaneous coronary intervention (PCT)
- Repeated cardiac surgery
- Cardiorespiratory arrest
- Cerebral hemorrhage
- Death

All serious unexpected adverse drug reactions will be reported to Health Canada as per ICH/GCP guidelines.

Unblinding

Unblinding for this study will occur when:

1. Clinical treatment decisions need to be made and when an unexpected serious adverse event occurs and the intervention must be made known.
2. At the request of the Data Safety Monitoring Committee.

Capital Health

3. After 110 participants have reached the primary endpoint for interim analysis.
4. At the conclusion of the study to determine the effect of the intervention.

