The Blood Transfusion Services are able to unblind for the clinical treatment of a patient. Please refer to the site Standard operating procedure for more details of this process. If a patient's treatment is unblinded before the 24 hour primary end point their data will not be used in the analysis.

STATISTICS

Sample size

The primary outcome of interest will be overall need for blood transfusion at 24hr after surgery (including all used blood components from the start of surgery). For the sample size calculations G*Power version 3.1.2 was used.

Based on the available literature ^{9,10,12}, the investigator hypothesized a 70-90% reduction in total units of blood products in the group receiving fibrinogen compared with the group receiving conventional therapy. An estimate of blood product requirement in the group receiving conventional therapy is mean 3.4 units (standard deviation 5.9) based on our data from 2005 to 2007 for AVR+CABG, MVR+CABG, AVR+MVR, and Aortic root repair +/-AVR. Standard deviation 5.9 was used for both groups. Blood product requirement in the two groups will be compared using the Mann-Whitney U test for two independent samples. The sample size calculation was based on a two-tailed test with $\alpha = 0.05$, for $\beta = 0.2, 0.1, \text{ and } 0.05$. The sample sizes shown Table 1 represent the number of patients required in each group.

Details of the planned analysis

~~Individual case forms will be completed by the research coordinator for individual patients.~~ **The research coordinator will complete individual case forms for individual patients.** These forms will be detailing demographic characteristics,

Capital Health

intra-operative, post-operative and follow-up outcomes. Outcome data and blood samples will be collected according a lab/data schedule (Table 2). ~~All data will be reviewed by the appropriate clinical outcomes committee.~~ **The Sponsor will review all data.** Once reviewed all data will entered and maintained electronically.

Primary outcome: Blood component requirement in the two groups will be compared using the Mann-Whitney U test for two independent samples.

Secondary outcomes: Univariate comparisons between patients randomized to FIB and patients randomized to PLACEBO group will be carried out based on pre-, intra-, and post-operative variables using Chi-square tests for dichotomous variables, two-tailed t-tests for continuous variables and Wilcoxon rank sum tests for nominal variables.

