CFT (clot formation time): time from initiation of clotting until a clot firmness of 20mm is detected
 => fibrin polymerisation, stabilisation of the clot with thrombocytes and F XIII

MCF (maximum clot firmness): firmness of the clot
 => increasing stabilisation of the clot by the polymerised fibrin, thrombocytes as well as F XIII

ML (maximum lysis): reduction of the clot firmness after MCF in relation to MCF
 => stability of the clot (ML < 15%) or fibrinolysis (ML > 15% within 1h)

Figure 2. FIBTEM® Test Specificities

[figure not shown]
[figure not shown]
FIBTEM:

- activation as in **EXTEM**
- platelet inhibition reagent added

TEMogram shows isolated fibrinogen contribution to Clot firmness

- A)
- **EXTEM:** amplitude low
 - **FIBTEM:** amplitude normal
- => fibrinogen level OK
=> platelet deficiency

- B)
- **EXTEM:** amplitude low
 - **FIBTEM:** amplitude low
- => fibrinogen deficiency

[figure not shown]
[figure not shown]

Figure 3. Treatment Algorithm

[figure not shown]

Table 1. Sample Size Calculation

	Relative Risk Reduction in Mean Number of Units Transfused			
Power = 1-beta	30% $\Delta = 1.0$ units (3.4 to 2.4)	50% $\Delta = 1.7$ units (3.4 to 1.7)	70% $\Delta = 2.4$ units (3.4 to 1.0)	90% $\Delta = 3.1$ units (3.4 to 0.3)
80%	634	220	111	69
90%	848	295	149	92
95%	1049	364	183	113

Table 2. Schedule of Assessments

	Preop I+II	Intraop I	Intraop II	Intraop III	Postop I	Postop II	Postop III	Postop IV
Time intervals	Baseline	On Bypass Aortic Clamp Off	Off Bypass After Heparin reversal (5-15 minutes post protamine)	10 minutes after administration (+5 minutes)	End of Surgery (+10 minutes)	Blood Draw 12 Hours (+60 minutes)	Blood Draw 24 Hours (+60 minutes)	Discharge
Primary Outcome					Total Blood Components Used	Total Blood Components Used	Total Blood Components Used	Total Blood Components Used
					Cryo Used	Cryo Used	Cryo Used	Cryo Used
					FFP Used	FFP Used	FFP Used	FFP Used
					Packed Red Cells Used	Packed Red Cells Used	Packed Red Cells Used	Packed Red Cells Used
					Platelets Used	Platelets Used	Platelets Used	Platelets Used
Secondary Outcomes	Fibrinogen Levels		Fibrinogen Levels	Fibrinogen Levels	Fibrinogen Levels	Fibrinogen Levels	Fibrinogen Levels	Adverse Effects
	Hematocrit		Hematocrit	Hematocrit	Hematocrit	Hematocrit	Hematocrit	Anaphylaxis

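### Patients still bleeding with FIBTEM above 20 mm are dropped from the primary analysis after randomisation, mainly from the fibrinogen arm as far as can be foreseen, which favours fibrinogen

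*Combined protocol and SAP*

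**What the plan says.** The rule is the product of two sections of the combined protocol and SAP.

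- **Subject withdrawal criteria.** The trigger is continued bleeding: "In case of an ongoing bleeding after step 3 of the study algorithm (Figure 3) an immediate and blinded FIBTEM is performed". The consequence is: "If the FIBTEM shows an amplitude > 20 mm the patient will be unblinded and drop out of the study for safety reasons". The purpose is given as: "This way it is ensured that a patient who received concentrated fibrinogen is not getting Cryoprecipitate".
- **Unblinding.** "If a patient's treatment is unblinded before the 24 hour primary end point their data will not be used in the analysis".

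Three other places bear on who is affected.

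- **Dosage and Dosage Regimen.** FIB patients are dosed back to their own preoperative FIBTEM MCF. There is a 10 g cap but no ceiling in mm. In the worked example, "The overall dose of concentrated fibrinogen to achieve the baseline MCF of 22 mm would be" 6.4 g, starting from 10 mm on bypass. Baselines of 12 mm or less are dosed to 15 mm. Placebo patients receive saline.
- **Post-operative management.** Diffuse bleeding is treated with blood components in steps 2 to 5 of the algorithm.
- **Table 2.** "Total Blood Components Used" is scheduled at end of surgery, 12 h, 24 h and discharge.

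The documents contain no intention-to-treat statement, no sensitivity analysis or imputation for these patients, and no expected number of such withdrawals.

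**The concern.** The exclusion depends on events after treatment. Only patients who are still bleeding are tested, and bleeding is what drives component use, the primary outcome. A patient who has passed step 3 has normally been transfused already, so the rule tends to take out heavy users.

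It is also unlikely to act equally in the two arms. Its stated aim is to protect patients who received the concentrate, the dose formula can carry those patients past 20 mm, and the test comes before Cryo (step 4), so a placebo patient has had neither concentrated source of fibrinogen from the algorithm. A placebo patient could exceed 20 mm, but this is much less likely.

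Removing heavy users from mainly one arm lowers that arm's counts with no drug effect. The error runs in the direction of the trial's hypothesis, so a positive result would be open to challenge.

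**Working it through.** **1. The plan's sample size.** Sample size and Table 1 give control mean 3.4 units, SD 5.9 in both arms, difference 2.4 units (70% reduction), two-sided alpha 0.05, 80% power and 111 per group. The standardised effect is 2.4/5.9 = 0.407. A two-sample noncentral t calculation gives 96 per group. With the minimum Mann-Whitney efficiency of 0.864 (an assumption about the software option used), it gives 111 per group and 80.0% power. The plan's figure reproduces, and 2 × 111 = 222 is the planned total. It includes no allowance for withdrawals.

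**2. Can the dose pass the cut-off?** In the worked example the dose is (22 − 10) × 75/140 = 6.43 g, stated as 6.4 g. The expected MCF is 10 + 6.4 × 140/75 = 21.9 mm, above 20 mm, and the 10 g cap does not bind. By formula alone, only patients with a baseline above 20 mm are targeted past the cut-off.

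**3. Effect on the false-positive rate.** Assumptions:

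- no drug effect, 111 per arm;
- negative binomial counts with mean 3.4 and SD 5.9, so k = 3.4²/(5.9² − 3.4) = 11.56/31.41 = 0.368 and P(0 units) = 0.42;
- removals in the FIB arm only, at random within the heaviest quarter (28 patients), the heaviest half (56) or all 111;
- tie-corrected Mann-Whitney test, interim look ignored, 20,000 simulated trials.

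The rates below are one-sided in favour of FIB; nominal is 2.5%. The reduction is the apparent fall in the FIB mean.

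| FIB patients removed | Heaviest quarter: rate | Reduction | Heaviest half: rate | Reduction | Unrelated to use: rate |
|---|---|---|---|---|---|
| 0 | 2.51% | none | 2.51% | none | 2.51% |
| 1 | 3.10% | 2% | 2.83% | 1% | 2.49% |
| 2 | 3.83% | 4% | 3.25% | 2% | 2.49% |
| 3 | 4.58% | 6% | 3.66% | 3% | 2.57% |
| 6 | 8.29% | 13% | 5.33% | 5% | 2.58% |
| 11 | 19.23% | 24% | 9.84% | 10% | 2.56% |

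The last row requires 11/28 = 39% of the heaviest quarter, or 11/56 = 20% of the heaviest half, to exceed 20 mm.

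**4. A second simulation with a different removal rule.** Under the same distribution, 20% of patients use 6 or more units. Over 6,000 trials, dropping 10%, 25% or 50% of those in the FIB arm removes on average 2.2, 5.6 or 11.1 patients. The spurious mean difference is −0.19, −0.50 or −1.02 units, and rejections favouring FIB are 3.9%, 8.4% or 20.7%, against about 2.4% with no removal. The two approaches agree.

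**5. Power is not the issue.** At the planned effect, with 106 or 100 FIB patients retained, power is 79.1% or 77.9%. The harm is bias.

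**The case against.** The strongest reply is that the rule may seldom fire. It needs continued bleeding and a FIBTEM above 20 mm together. The formula only restores the patient's own baseline, enrolment is limited to preoperative fibrinogen of 3.8 g/l or less, and the 22 mm baseline is a calculation example, not evidence that such baselines are common. This stands: the frequency is unknown in both arms.

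Second, Figure 3 is not shown, so the amounts given in steps 2 and 3 cannot be seen. Patients who go on to steps 4 and 5 may use more than those stopped at the cut-off. The heaviest-half figures are therefore at least as defensible as the heaviest-quarter ones, and they are milder. This also stands.

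Third, the rule as written covers both arms. If 2 placebo patients were removed along with 6 FIB patients, a 6,000-trial check gives 5.8% for the heaviest quarter (7.8% in the same check with FIB removals only) and 4.4% for the heaviest half (5.5%). Some placebo removals shrink the bias but do not abolish it.

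Finally, one may say that safety requires the withdrawal. Safety requires the test, the unblinding and the withholding of Cryo. It does not require discarding the outcome. Unblinding may influence later transfusion, but exclusion also throws away components given before it. The expected loss under 5% in Estimated Recruitment Rate is no answer, since it concerns 6-month follow-up.

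**Conclusion.** The concern holds. Read together, the two sections require randomised, treated patients to be left out of the primary analysis because of a close precursor of the outcome, and nothing elsewhere in the documents offsets this. That the exclusions fall mainly in the FIB arm is an inference from the stated purpose, the dosing target and the position of the test before Cryo. It is well supported but not documented, so confidence is medium.

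The size is conditional. One or two removals matter little. About 5% of the FIB arm (6 of 111) gives a one-sided error rate between 5.3% and 8.3%, and about 10% (11 of 111) between 9.8% and 19%. These figures rest on the negative binomial shape, on the 2005 to 2007 mean and SD, on FIB-only removal and on no drug effect. Even the largest apparent reduction, 24%, is well short of the 70% the trial is powered for, so the main risk is a false or exaggerated positive finding. This should be corrected before analysis.

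**What to change.** Leave the clinical action in Subject withdrawal criteria as it is: FIBTEM check, unblinding, no Cryo above 20 mm. Neither the dose formula nor the threshold needs to change. Amend that section and Unblinding to read along these lines:

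> Patients unblinded or withdrawn under the FIBTEM > 20 mm rule remain in the primary analysis in their randomised group, with all components counted from start of surgery to 24 h after study drug.

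Report the number of such patients by arm. An analysis without them may be kept as a sensitivity analysis.

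The cost is wording in two sections, because Table 2 already schedules the counts at end of surgery, 12 h and 24 h. In the simulation, keeping everyone in gives the nominal 2.5%. This wording does not reach patients unblinded before 24 h for other reasons, such as an unexpected serious adverse event. The sentence in Unblinding still excludes them, and the sponsor should consider the same treatment for them.

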The test compound will be administered through the central line (usually internal jugular vein catheter) within 10 minutes (25-50 ml/minute) by the anesthesiologist. Since high doses of anticoagulants are used in this surgical population while on cardiopulmonary bypass it is important that the test compound is administered in a relatively short period of time to boost the fibrinogen level. Two studies in cardiac surgery used an infusion rate of 20ml/minute and 150ml/minute without any adverse events.^{25,26}

This bolus approach interrupts the circle of hemodilution and ongoing bleeding produced from cardiopulmonary bypass. This is the practice at CDHA in the cardiovascular anesthesia group. This technique has not produced any thromboembolic complications or severe side effects in the 25+ patients that have received this product in our health centre.

Reconstitution

The RiaSTAP, and placebo, are labelled as per Health Canada regulations. The reconstituted RiaSTAP or placebo will be transported by the ~~the Research Coordinator~~ **Study drug designate** to the OR and the Blood Transfusion requisition will be signed and completed by the anesthesiologist and the ~~Research Coordinator~~ **Study drug designate** once the medication has been given.

PLANNED FREQUENCY AND DURATION OF FOLLOW-UP

In-Hospital Follow-Up

All postoperative cardiac surgery patients will be followed for the duration of their hospital stay. Blood work and amount of blood components and products will be assessed at end of surgery, 12hr and 24hr after administration of study medication or placebo. The study endpoint for the primary outcome parameter (amount of blood components) will be **24h after administration of study medication or placebo**.

Other outcomes assessed include Thromboelastometry (ROTEM[®], CT, CFT, Angle, MCF), CVICU-stay, Hospital-stay, In-Hospital Mortality, Hemoglobin, and adverse events.

After Discharge Follow-up

After discharge from hospital all patients, ~~including those involuntarily withdrawn from the study by a member of the research team,~~ are followed-up in clinic six weeks postsurgery. This is currently the standard of care for patients post CABG surgery. If ~~the patient~~ a **study participant** does not return to

Capital Health

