After weaning from cardiopulmonary bypass (CPB), completion of heparin reversal with protamine and surgical hemostasis either concentrated fibrinogen or saline will be given intravenously. The surgeon and anaesthesiologist will ~~the amount of blood loss that is considered diffuse (non-surgical) bleeding.~~ **determine when surgical hemostasis is completed.** After agreement **on completion of surgical hemostasis and defined intraoperative conditions** a transfusion algorithm is initiated (Figure 3). ~~After the surgeon and anesthesiologist have agreed on diffuse bleeding then the patients are randomized~~ FIB patients are treated with concentrated fibrinogen based on maximum clot firmness (MCF) in the FIBTEM test (Figures 1 and 2) performed on CPB (aortic cross clamp off).

Defined Intraoperative Conditions - Standard of Care Assessments

As per the usual standard of care/clinical assessment to treat, the following criteria must be met prior to Fibrinogen administration:

Capital Health

- ACT less than 150s,
- body temperature higher than 36–35.5°C,
- pH more than 7.3,
- hemoglobin level higher than 70g/l,
- calcium level higher than 1 mmol/l (ionized)) and
- ~~no blood products given before or during CPB (Defined intraoperative conditions).~~

Anaesthesia management

As per the standard of care in this surgical population, all patients will undergo general anaesthesia and will be induced with midazolam, fentanyl or sufentanil, propofol and rocuronium. General anaesthesia will be maintained with sevoflurane titrated to maintain an end-tidal concentration of 1-2% and boluses of fentanyl or sufentanil, until initiation of cardiopulmonary bypass.

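### Data from patients unblinded before 24 hours are left out of the analysis with no exception for safety, and follow-up after withdrawal is not defined

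*Combined protocol and SAP*

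**What the plan says.** **Exclusion rule.** The last sentence of Unblinding (Assessment of Safety) says that when a patient's treatment is unblinded before the 24-hour primary endpoint, that patient's data are not used in the analysis. It does not say which analysis.

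**Routes to unblinding.** The same section allows unblinding when treatment decisions are needed and "when an unexpected serious adverse event occurs and the intervention must be made known". Under Subject withdrawal criteria, a patient still bleeding after step 3 of the algorithm has a FIBTEM test. If the amplitude exceeds 20 mm, "the patient will be unblinded and drop out of the study for safety reasons". The stated aim is that a patient who received fibrinogen concentrate does not also get cryoprecipitate.

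**Planned harm comparison.** Adverse events (anaphylaxis, stroke, myocardial infarction, pulmonary embolism, deep vein thromboembolism) are secondary outcomes in both the objectives and the Trial Design section. Details of the planned analysis gives chi-square tests between arms for dichotomous secondary outcomes.

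**Capture and withdrawal.** Assessment of Safety states: "The following treatment-emergent and adverse effects will be captured during this study from the date", continuing after struck words with "of randomization to the 6 month follow-up". Air embolism is on its list. Under Subject withdrawal criteria, "Patients who have extremely rare complications like air embolism, heart perforation or heart lung machine failure will be" withdrawn.

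**Follow-up.** After Discharge Follow-up still sends all patients to a six-week clinic visit and has all of them contacted at three and six months. The words "including those involuntarily withdrawn from the study by a member of the research team" are struck out. The phone visit for a missed clinic date now refers to a study participant instead of the patient.

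**The concern.** The exclusion is tied to an event that happens after dosing and can itself be caused by harm. A serious reaction that leads to unblinding within 24 hours would, on the plain wording, take the patient out of the comparison in which that reaction should count. The FIBTEM route depends on the fibrinogen response, so it would act mainly on one arm.

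The Risks section says that no published study clearly addresses the risk of fibrinogen supplementation. With about 111 patients per arm, one or two missing events can change how the safety table reads. No safety population is defined that would override the exclusion.

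**Working it through.** No rate of early unblinding or withdrawal is given, so the main check sets the sections side by side.

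1. **Arm size, used only as a denominator.** Table 1 gives 111 per group for a difference of 2.4 units, SD 5.9, two-sided alpha 0.05 and 80% power. Normal approximation: 2 × (1.960 + 0.842)² × 5.9² / 2.4² = 94.9. Dividing by 0.864, the minimum efficiency of the Mann-Whitney test, gives 109.8. The same calculation with the noncentral t gives 111. The figure reproduces, and 2 × 111 = 222 is the planned total.

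2. **Which triggers fall after dosing?** Treatment of Subjects says that after weaning from bypass, "completion of heparin reversal with protamine and surgical hemostasis either concentrated fibrinogen or saline will be given intravenously".
   - Patients with surgical bleeding "with requirement of a second pump run are withdrawn from the study"; this would mostly come before dosing. So would heart-lung machine failure and, mostly, heart perforation.
   - Air embolism could fall on either side.
   - The FIBTEM check follows the study drug: its stated aim is to prevent fibrinogen overdosing, and Post-operative management describes steps 2 to 5 as blood components.
   - Unblinding for an unexpected serious event can also follow dosing.

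3. **Which arm?** The FIBTEM rule is worded for both arms, but its stated purpose concerns fibrinogen recipients. Dosage and Dosage Regimen aims to restore the baseline clot firmness, and its worked example targets 22 mm, above the 20 mm limit. A patient who reached that target and was still bleeding after step 3 would be dropped. The example is illustrative and gives no frequency.

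4. **Combining the rules.** Either route, if it occurs before 24 hours, meets the exclusion condition. Adverse events are outcomes with planned between-arm tests, so the exclusion reaches them unless it is limited.

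5. **Size.** Let f be the fraction of dosed patients excluded and k their event risk relative to the rest. Share of events lost = f·k / (f·k + 1 − f).
   - With k = 1 the share is f. An assumed f of 3% to 10% (about 3 to 11 of 111) loses 3% to 10% of events.
   - With an assumed k = 5 (20% against 4%), f = 3% gives 0.60/4.48 = 13% and f = 10% gives 2.0/5.6 = 36%.
   - The result turns on k, which the documents do not give.

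6. **Precision or selection?** For an event never seen, the upper 95% bound is 1 − 0.05^(1/n). With n = 111 it is 2.66%; with 10% of the arm missing (n = 99.9) it is 2.95%. Lost precision is minor. Selection is the issue: as a hypothetical case, two events in 111 (1.8%) that both led to early unblinding would be reported as 0 of 109.

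7. **Follow-up after withdrawal.** No section says that event capture stops at withdrawal, and none says that it continues.

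**The case against.** The strongest reply is that the exclusion is tied to the 24-hour primary endpoint, so its authors probably meant the primary analysis only. That reading is natural, but the text does not say it. Individual cases are also preserved elsewhere: drug-related events go to the Data and Safety Monitoring Committee, and serious unexpected reactions go to the regulator. This protects case review, not the comparison between arms.

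A reader might infer several stronger points that the documents do not support:

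- **That withdrawal ends the safety record of dosed patients.** The current text still covers all patients at six weeks, three months and six months. The 6-month database link is also for all patients, the capture window has no exception for withdrawals, and deaths in the province are tracked. A struck phrase supports only an inference, and the change to study participant may be terminology. What stands is that no rule settles the matter. The items listed for the 6-month link (cardiac mortality, readmission, re-intervention) do not include stroke, pulmonary embolism, deep vein thromboembolism or anaphylaxis.
- **That the two uses of air embolism contradict each other.** An event can be recorded and also lead to withdrawal. What is missing is a statement of what follows.
- **That patients above 20 mm have the largest drug effect and tell most about harm.** A high amplitude may reflect a high baseline.
- **That anaphylaxis would vanish entirely.** It is a pre-listed outcome, and nothing says that it must lead to unblinding.
- **That 13% to 36% of serious events would be lost.** This range depends wholly on assumed rates and on every such event being lost.

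**Conclusion.** The point holds as a defect of wording with a real analytic consequence. Followed literally, the early-unblinding rule removes dosed patients from the adverse event comparison for reasons linked to harm or to fibrinogen response, and mainly from the fibrinogen arm. The conclusion about the arm rests on the stated purpose of the FIBTEM rule, not on data.

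The size cannot be stated. If excluded patients carried average risk, the proportion of events lost would equal the proportion excluded. It would be larger if their risk were higher, as it is by construction when a serious event caused the unblinding. Continued safety follow-up after withdrawal is ambiguous, not abolished. Severity: should be fixed.

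**What to change.** - In Unblinding, limit the exclusion so that it never applies to safety outcomes.
- In Details of the planned analysis, define a safety set of every patient who received study drug or placebo, analysed by allocated arm whatever the later unblinding or withdrawal.
- In Subject withdrawal criteria and After Discharge Follow-up, state that withdrawal does not end adverse event capture to 6 months, and that the phone visit for a missed clinic date also covers withdrawn patients.
- Reconcile these sections with Assessment of Safety and the database-link text, and say how air embolism is handled as both a withdrawal reason and a captured event.

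No change to the clinical withdrawal or unblinding criteria is proposed. The cost is protocol wording and perhaps a few extra phone contacts, because the contact schedule and database link already exist.
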